8.5 Stopping Rules

The study will be stopped immediately if any patient suffers *at least one* of the following events during the course of the study, unless it can be shown that this event was unrelated to participation in the clinical trial:

- 1) Death
- 2) Upper limb paralysis or weakness
- 3) Bulbar weakness
 - a. Blurred vision
 - b. Facial paralysis
 - c. Dysarthria
- 4) Anaphylactic reaction
- 5) Any severe adverse drug reaction

The study will be stopped if the absolute difference in the surgical site infection (SSI) rate is 15% higher in one treatment group as compared to the other treatment group. The study statistician will compare the SSI rates in a blinded fashion on a periodic basis and notify the Principle Investigator of this information. The study team will review the data and notify the DSMB accordingly.

8.6 Medical Monitoring

It is the responsibility of the Sponsor-Investigator to oversee the safety of the study. This safety monitoring will include careful assessment and appropriate reporting of adverse events as noted

above, as well as the construction and implementation of a site data and safety-monitoring plan (see section 10 “Study Monitoring, Auditing, and Inspecting”). Medical monitoring will include a regular assessment of the number and type of serious adverse events.

8.6.1 Internal Data and Safety Monitoring Plan

A Trial Steering Committee will include the Principle Investigator and site specific study representatives. The statistician, other study personnel and collaborators will be welcome to contribute and will be included as needed. The committee will meet every other month during data collection and as needed until the trial is completed. These meetings will be used to discuss data management and analysis, evaluate progress of the trial, review study recruitment and to troubleshoot any issues and/or administrative problems as they arise.

An internal Data Safety and Monitoring Plan (DSMP) will allow identification of adverse events and accrual problems. A Mayo Clinic statistician to be named who is not involved with this project will review the unblinded adverse event data to assess safety, integrity of the data collected and efficacy after 1/2 of the target sample size has accumulated. At the interim analysis, the pooled PRO data will be reviewed in order to assess sample size and determine if sample size adjustment is necessary. At this time, any safety concerns or grounds for early stopping also will be reviewed. In addition, patient safety will be protected by open communication and reporting of patient safety concerns by any personnel involved in the study to the principal investigator or Trial Steering Committee members during the course of patient participation in the study. If significant issues arise they will be reported to the institutional IRB for further consideration.

8.6.2 Independent Data and Safety Monitoring Board

Data Safety and Monitoring Board (DSMB): An independent Data Safety and Monitoring Board will consist of [name], [name], [name], [name], [name], [name] and a Mayo Clinic statistician who is not involved with this project. The Data Safety Monitoring Board will assess safety and efficacy at interim analysis (when 75 patients have been enrolled). The Board will be empowered to recommend continuation, modification, or early closure of the trial. Recommendations of the Data Safety Monitoring Board will be reviewed by the Steering Committee who will make the final decision to terminate accrual early. In addition, patient safety will be protected by open communication and reporting of patient safety concerns by any personnel involved in the study to the principal investigator or Trial Steering Committee members during the course of patient participation in the study. If significant issues arise they will be reported to both institutional IRBs for further consideration.

9 Data Handling and Record Keeping

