Confidentiality Safeguards: Participants will be notified that information collected during their participation in this study is considered confidential. All data gathered in the study will be de-identified and kept in a password-protected study-specific database at Mayo Clinic. Confidentiality of each participant's data will be protected with all data identified solely by a code number. Names will not be connected to any information. Only the authors of the study will have access to this information, and patient details will be filed under code number, not under patient name. A list matching subject names and code numbers will be maintained on a separate sheet of paper kept in locked storage; only the authors of the study will have access to this information. This information will be kept on a computer in a locked departmental office at all times. Information from any woman who is enrolled but later determined to be ineligible will be retained in a confidential electronic data base.

Sources of Materials: Participants' responses to the NPIS and the BREAST-Q® will be the main source of research material. Patient information will also be obtained from existing electronic medical records. These data will be collected for research purposes only and not used for any other purposes.

Data Safety and Monitoring Plan (DSMP): A Data Safety and Monitoring Plan (DSMP) will allow us to identify adverse events and accrual problems. A statistician will review the unblinded adverse event data after 1/2 of the target sample size has accumulated.

Data Safety and Monitoring Board (DSMB): An independent Data Safety and Monitoring Board will consist of [name], [name], [name], [name], [name], [name] and a Mayo Clinic statistician who is not involved with this project. The Data Safety Monitoring Board will assess safety and efficacy at interim analysis (when 75 patients have been enrolled) and whenever necessary.

Median Lethal Dose:

The median lethal dose is estimated to be approximately 39 units of BTX-A per kilogram of body weight.²⁶

Safety, Risks and Adverse Effects:

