7.1 Sample Size Determination

The *primary study endpoint* is to determine the efficacy of a single intra-operative injection of BTX-A in the pectoralis major muscle on pain and physical well-being in women undergoing tissue expansions following mastectomy and immediate tissue expander breast reconstruction.

Secondary study endpoints include:

- 1) The initial percent volume expansion (defined as initial intraoperative fill volume divided by manufacturer recommended total tissue expander volume);
- 2) The rate of tissue expansion between the BTX-A groups and the placebo and control groups, with or without the use of ADM;
- 3) Rate of reconstructive failure (tissue expander removal for reasons such as infection or uncontrolled pain).

The *primary safety endpoints* of this study is the incidence of side effects attributable to the injection of BTX-A at doses of 100 units and 200 units, in women undergoing immediate post-mastectomy breast reconstruction with tissue expander(s).

Power and Sample Size: The only available preliminary data for the effect of BTX-A use on pain during initial tissue expansion were obtained from Layeeque et al, *Annals of Surgery* 2004. In this retrospective study, pain was scored using a visual analog scale ranging from 0 to 10, with higher scores indicating increased pain. Layeeque et al reported a mean \pm standard deviation (SD) pain score during initial tissue expansion of 1.95 ± 1.88 for the BTX-A group compared with 5.61 ± 2.77 for the non- BTX-A group.

Sample size estimates were obtained assuming 80% power and a significance level of 0.05 for a two-sample t-test to test the effects of BTX-A use on pain during initial tissue expansion. The table below (entitled Sample Size Estimates) summarizes the sample size needed in each group to achieve approximately 80% power. We calculated the sample sizes needed to detect a 50% decrease in the mean pain scores (assuming mean pain scores for the BTX-A and non-BTX-A groups of 2.0 and 4.0) and a 25% decrease in mean pain scores (assuming mean pain scores for the BTX-A and non-BTX-A groups of 3.0 and 4.0). Sample sizes were calculated assuming low, moderate, and high SDs of 2.0, 2.5, and 3.0, respectively. For example, if mean pain scores for the BTX-A and non-BTX-A groups

were 3.0 and 4.0, respectively, with a moderate SD of 2.5, 100 patients in each group, for a total of 200, would be required to detect this difference as statistically significant.

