In order to minimize cost while still maintaining scientific integrity, our goal is to accrue up to 134 patients in order to obtain 128 complete data sets (64 patients per study arm). If the accrual rate was slower than anticipated, we would extend the enrollment period and continue to accrue patients until sample size requirements were met. If the required number of enrolled subjects was not met for any reason, we would end the study and analyze the data using the same techniques. An appropriate cautionary statement would be added to the discussion section of any publication.

SAMPLE SIZE ESTIMATES

BTX-A	Mean Pain	SD	N per Group
No	4.0	2.0	17
Yes	2.0		
No	4.0		64
Yes	3.0		
No	4.0	2.5	26
Yes	2.0		
No	4.0		100
Yes	3.0		
No	4.0	3.0	37
Yes	2.0		
No	4.0		143
Yes	3.0		

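### The interim review has two conflicting triggers, and the plan does not say whether it can close the trial for efficacy or by what boundary

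*Combined protocol and SAP*

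**What the plan says.** Two sections of the combined protocol and SAP schedule the interim review, and the Human Subjects part of the Introduction repeats both.

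- **Section 8.6.1.** A statistician outside the project reviews unblinded adverse event data to assess safety, data integrity and "efficacy after 1/2 of the target sample size has accumulated". Pooled patient-reported data are used to reconsider the sample size, and grounds for early stopping are reviewed at the same time.
- **Section 8.6.2.** "The Data Safety Monitoring Board will assess safety and efficacy at interim analysis (when 75 patients have been enrolled"). Then: "The Board will be empowered to recommend continuation, modification, or early closure of the trial". The Steering Committee, which includes the principal investigator, makes the final decision.
- **Introduction.** The half-target review is described as covering adverse event data, with no mention of efficacy. The Board's assessment of safety and efficacy takes place "at interim analysis (when 75 patients have been enrolled) and whenever necessary".

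On the target, section 7.1 says "our goal is to accrue up to 134 patients in order to obtain 128 complete data sets (64 patients per study arm"). On the error rate it says "Sample size estimates were obtained assuming 80% power and a significance level of 0.05 for a two-sample t-test". Section 7.2 plans ordinary two-sample tests with no allowance for interim looks. The stopping rules in section 8.5 concern safety events and surgical site infection only.

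**The concern.** Seventy-five is not half of any target stated in section 7.1, and the two triggers count different things: sample size accumulated in one place, women enrolled in the other. A reader cannot tell when the formal interim review is due, who is responsible for it, or whether it happens once or twice.

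A body that sees efficacy and can recommend closure needs either a boundary or a statement that efficacy is not a ground for closure. The plan has neither. If a favourable interim result could end the trial, or be claimed as a finding, at the ordinary level, the 0.05 used for planning would no longer describe the trial's false-positive rate. The open-ended provision for further Board meetings leaves the number of such looks without a limit.

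**Working it through.** **Inputs.** Target 134 accrued and 128 complete, 64 per arm; level 0.05; power 80% (section 7.1). Triggers: half the target (Introduction, section 8.6.1) and 75 enrolled (Introduction, section 8.6.2). Accrual 40 months with 4 months of follow-up per woman (section 3.1).

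**1. The plan's own figure.** Section 7.1 considers "a 25% decrease in mean pain scores (assuming mean pain scores for the BTX-A and non-BTX-A groups of 3.0 and 4.0"). It adds: "Sample sizes were calculated assuming low, moderate, and high SDs of 2.0, 2.5, and 3.0, respectively". With difference 1.0 and SD 2.0, the normal approximation is n = 2 × (1.96 + 0.84)² × 2.0² / 1.0² ≈ 62.8, or 63 per arm. The exact two-sided t-test gives 63.77, which rounds up to the stated 64. The target reproduces with a single final test at two-sided 0.05, so nothing was reserved for an interim look.

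**2. The triggers.**
- Half the target: 134/2 = 67, or 128/2 = 64.
- Board trigger: 75/134 = 56.0%; 75/128 = 58.6%.
- Gap: 75 − 67 = 8 to 75 − 64 = 11 women.

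**3. Calendar, assuming uniform accrual.** 134/40 = 3.35 women per month.
- 67 enrolled: 67/3.35 = month 20.0.
- 75 enrolled: 75/3.35 = month 22.4. Of these, about 4 × 3.35 = 13 have under four months of follow-up, leaving about 62.
- 67 with four months completed: 67/3.35 + 4 = month 24.0, with about 24 × 3.35 = 80 enrolled.

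**4. Type I error if each look could declare efficacy at two-sided 0.05.** Under the null hypothesis, the test statistics at looks with n₁ and n₂ women are standard normal with correlation √(n₁/n₂). With f = n₁/n₂ and interim critical value c:

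error = 1 − ∫ from −c to c of φ(z) × [Φ((1.96 − √f·z)/√(1−f)) − Φ((−1.96 − √f·z)/√(1−f))] dz

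| Looks | Error, one endpoint |
|---|---|
| Half, then final (f = 0.50, c = 1.96) | 8.3% |
| 75 of 134, then final (f = 0.56) | 8.1% |
| 75 of 128, then final (f = 0.586) | 8.0% |
| 67, 75 and 134 (three correlated statistics) | 9.4% |
| 64, 75 and 128 | 9.5% |

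Simulation agrees with these values. One unadjusted look adds about 3 points to the nominal 5%. A second adds a further 1.1 to 1.5 points (9.4 − 8.3 = 1.1; 9.5 − 8.0 = 1.5).

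**5. With a strict interim threshold.** p<0.001 at a single look at half the target, with the final test at 0.05, gives about 5.02% by the formula and about 5.03% by simulation.

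**The case against.** Three stronger readings are tempting, and the documents do not support them.

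- **That two bodies can each close the trial.** Only the Board is given power to recommend closure. The statistician in section 8.6.1 reviews grounds for stopping and is given no such power.
- **That the plan prescribes two unblinded efficacy looks.** At half target, section 8.6.1 names adverse event data as what is unblinded, and the patient-reported data are pooled. Both primary outcomes are patient-reported, and pooled data give no treatment comparison. The Introduction limits that review to adverse events. Sections 8.4, 8.6.1 and 8.6.2 each speak of one interim analysis, and the uninvolved statistician may be the one who sits on the Board. A single look described inconsistently is equally plausible.
- **That the 0.05 level is already broken.** Inflation needs a look that can stop for, or claim, efficacy. Stopping for safety or futility alone does not inflate the error, and the only stopping rules written down are for safety.

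Two further points have force. Day-to-day safety protection does not wait for the interim: section 8.4 provides for immediate unblinding after an adverse event, and section 8.5 applies throughout. Incomplete four-month follow-up also matters less than it seems, because the trial is powered on pain at initial expansion and visits begin in week 1 to 2, so most recent enrollees would already have those data.

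These points narrow the concern without removing it. The triggers still disagree, the Introduction and section 8.6.1 still differ on whether efficacy is in scope, and the Board still assesses efficacy and may recommend closure without a boundary.

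**Conclusion.** The concern holds in a limited form. The triggers conflict (67 or 64 versus 75), the scope of the half-target review is described in two ways, and the consequence of the Board's efficacy assessment is undefined.

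The size is conditional. If the interim can stop for or claim efficacy at p<0.05, type I error is about 8.1% to 8.3% with one look on the 134 basis (8.0% for 75 of 128). It is about 9.4% only if both triggers lead to separate efficacy looks. If efficacy cannot stop the trial, there is no inflation and the remaining defect is the unclear timing and ownership of the review.

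The figures assume a two-sided level (sidedness is not stated, but two-sided reproduces the sample size table), information proportional to the number of women, and one endpoint. The plan has two primary outcomes and three primary hypotheses, and unscheduled efficacy looks are also possible; either would add to the error. The calendar figures assume uniform accrual.

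**What to change.** - Reconcile the Introduction, section 8.6.1 and section 8.6.2 to one trigger in one counting unit, for example 67 women enrolled (half of 134). Waiting for 67 women to complete four months would move the review to about month 24, later than 67 enrolled (month 20) or 75 enrolled (month 22.4).
- Have the independent statistician prepare one report for the Board, and say whether it contains efficacy by arm.
- State that additional Board reviews cover safety only.
- Either state that the interim cannot close the trial for efficacy, or allow it only at p<0.001 on a named primary outcome at that single look, with the final test at 0.05 (overall about 5.03%). If exactly 5% is wanted, an O'Brien-Fleming boundary with one look at half uses 0.0052 at the interim and 0.0480 at the end.

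The cost is protocol wording, with no added patients. The downside is that early closure for benefit would be ruled out or would need very strong evidence. At 67 enrolled, about 13 women would also have under four months of follow-up, so the named outcome should be one available early.

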9.1 Confidentiality

Information about study subjects will be kept confidential and managed according to the requirements of the Health Insurance Portability and Accountability Act of 1996 (HIPAA). Those regulations require a signed subject authorization informing the subject of the following:

- What protected health information (PHI) will be collected from subjects in this study
- Who will have access to that information and why
- Who will use or disclose that information
- The rights of a research subject to revoke their authorization for use of their PHI.

In the event that a subject revokes authorization to collect or use PHI, the investigator, by regulation, retains the ability to use all information collected prior to the revocation of subject authorization. For subjects that have revoked authorization to collect or use PHI, attempts should be made to obtain permission to collect at least vital status (long term survival status that the subject is alive) at the end of their scheduled study period.

Confidentiality Safeguards: Participants will be notified that information collected during their participation in this study is considered confidential. All data gathered in the study will be de-identified and kept in a password-protected study-specific database at Mayo Clinic. Confidentiality of each participant's data will be protected with all data identified solely by a code number. Names will not be connected to any information. Only the authors of the study will have access to this information, and patient details will be filed under code number, not under patient name. A list matching subject names and code numbers will be maintained on a separate sheet of paper kept in locked storage; only the authors of the study will have access to this information. This information will be kept on a computer in a locked departmental office at all times. Information from any woman who is enrolled but later determined to be ineligible will be destroyed.

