4.3 Subject Recruitment, Enrollment and Screening

Potential research subjects will be identified by a member of the patient's treatment team, the principal investigator, or research team at Mayo Clinic. If the investigator is a member of the treatment team, s/he will screen their patient's medical records for suitable research study participants and discuss the study and their potential for enrolling in the research study.

During the initial conversation between the investigator/research staff and the patient, the patient may be asked to provide certain health information that is necessary to the recruitment and enrollment process. The investigator/research staff may also review portions of their medical records at Mayo Clinic in order to further assess eligibility. They will use the information provided by the patient and/or medical record to confirm that the patient is eligible, and to contact the patient regarding study enrollment. If the patient turns out to be ineligible for the research study, the research staff will destroy all information collected on the patient during the initial conversation and medical records review, except for any information that must be maintained for screening log purposes. In most cases, the initial contact with the prospective subject will be conducted either by the treatment team,

investigator or the research staff working in consultation with the treatment team. The recruitment process outlined presents no more than minimal risk to the privacy of the patients who are screened and minimal PHI will be maintained as part of a screening log.

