4.4 Early Withdrawal of Subjects

4.4.1 When and How to Withdraw Subjects

Study participants may be withdrawn from the study prior to the subject completing all of the study related procedures, for the following reasons:

- Ineligibility unknown at the time of enrollment (e.g., inability to proceed with tissue expander reconstruction at the time of mastectomy)
- Nonadherence of enrolled subjects to protocol requirements
- Occurrence of competing events (e.g., patient's best interests)

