4.4.2 Data Collection and Follow-up for Withdrawn Subjects

Data collected on study subjects up to the time of withdrawal will remain in the study database and will not be removed, in order for the study to be scientifically valid. If a subject withdraws from the study, removal of already collected data would undermine the scientific, and therefore the ethical, integrity of the research. Such removal of data could also put enrolled subjects, future subjects, and eventual users of marketed products at an unreasonable risk.

Reasonable attempts to follow-up with study participants will be made by the research team. The Principal Investigator will ask each enrolled woman who is withdrawing whether she wishes to provide continued follow-up and further data collection subsequent to her withdrawal from the interventional portion of the study. Under this circumstance, the discussion with the subject would distinguish between study-related interventions and continued follow-up of associated clinical outcome information, such as successful completion of breast reconstruction, obtained through non-invasive chart review, and address the maintenance of privacy and confidentiality of the subject's information.

If a subject withdraws from the interventional portion of a study and does not consent to continued follow-up of associated clinical outcome information, the principal investigator will not access for purposes related to the study the subject's medical record or other confidential records requiring the subject's consent. However, an investigator will review study data related to the subject collected prior to the subject's withdrawal from the study, and will consult public records, such as those establishing survival status.

5 Study Drug

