5.9.4 Return or Destruction of Study Drug

At the completion of the study, there will be a final reconciliation of drug shipped, drug consumed, and drug remaining. This reconciliation will be logged on the drug reconciliation form, signed and dated. Any discrepancies noted will be documented and investigated, prior to return or destruction of unused study drug. Drug destroyed on site will be documented in the study files.

6 Study Procedures

TABLE OF VISITS:

	Research activity	Subject activity
Preoperative evaluation/Surgical listing appointment	Study Coordinator (SC) reviews the study with eligible patients and obtains informed consent	Complete the BREAST-Q and Numeric Pain Intensity Scale
Surgery	Randomization by site specific research pharmacy and intra-operative injection of study drug by plastic surgeon	•
First post-operative visit: • Week 1- 2	SC facilitates completion of questionnaire and assesses for adverse events	Complete the BREAST-Q and Numeric Pain Intensity Scale
Subsequent Plastic Surgery Appointments/Expansion Visits • Beginning at week 2-3 and intervals thereafter as determined by the plastic surgeon	SC facilitates completion of questionnaire and assesses for adverse events	Complete the BREAST-Q and Numeric Pain Intensity Scale
• End of Study • The last plastic surgery appointment prior to removal of the TE, or the date of TE removal (whichever occurs last within the 4 month postoperative period)		

Tissue expander placement: The surgical procedure for submuscular placement of the tissue expander will be performed in the usual manner by each participating plastic surgeon.

BTX-A Injection Protocol: see Section 5.4

Outcome Assessment: The outcome measures selected to test our working hypothesis and answer our specific aim #1 are a numeric pain intensity scale (NPIS)⁷¹, and the Physical Well-Being scale of the BREAST-Q®: Reconstruction Module. These two measures will be administered to study participants at the pre-operative visit, the first postoperative visit (1-2 weeks), and subsequent Plastic Surgery appointments/expansion visits until the end of the study is reached.

7 Statistical Plan

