7.3 Subject Population(s) for Analysis

The subject populations whose data will be subjected to the study primary and secondary analyses will include all randomized populations.

8 Safety and Adverse Events

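### Section 9.1 orders destruction of data on women found ineligible after enrolment, contradicting the Introduction, 4.4.2 and the all-randomised analysis set in 7.3

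*Combined protocol and SAP*

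**What the plan says.** Five places in the combined protocol and SAP bear on the data of a woman who is enrolled and later found ineligible.

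- Section 9.1, Confidentiality, last sentence: "Information from any woman who is enrolled but later determined to be ineligible will be destroyed".
- Section 1, Introduction, Human Subjects, the Confidentiality Safeguards paragraph, which otherwise matches 9.1 almost word for word: "Information from any woman who is enrolled but later determined to be ineligible will be retained in a confidential electronic data base".
- Section 4.4.1 lists this among the reasons for which a participant may be withdrawn: "Ineligibility unknown at the time of enrollment (e.g., inability to proceed with tissue expander reconstruction at the time of mastectomy").
- Section 4.4.2 on withdrawn participants: "Data collected on study subjects up to the time of withdrawal will remain in the study database and will not be removed". It gives its reason: "removal of already collected data would undermine the scientific, and therefore the ethical, integrity of the research".
- Section 7.3: "The subject populations whose data will be subjected to the study primary and secondary analyses will include all randomized populations".

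On timing, the table of visits in section 6 puts consent and the baseline questionnaires at the preoperative visit, and at the surgery row it has: "Randomization by site specific research pharmacy and intra-operative injection of study drug by plastic surgeon".

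Section 4.3 has its own destruction rule for patients who turn out to be ineligible at recruitment: "the research staff will destroy all information collected on the patient during the initial conversation and medical records review", apart from what a screening log needs. That concerns screening before enrolment and is not part of the conflict.

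**The concern.** Staff cannot obey both 9.1 and the Introduction, and nothing in the documents says which prevails. The choice matters because destruction, unlike an analysis decision, cannot be reversed later by a sensitivity analysis.

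If the woman had already been randomised, destroying her data excludes her after randomisation on the strength of a confidentiality clause. Her questionnaires could no longer be analysed in the set that 7.3 defines. If she had also been injected, study adverse-event data on an exposed participant could go too. The incidence of side effects is the primary safety endpoint (3.4), section 8.2 requires every adverse event in the study period to be recorded, and section 8.5 has a stopping rule that compares surgical site infection rates between arms. Section 9.4 also requires study records to be kept for years.

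**Working it through.** **1. The plan's own figure.** Section 7.1 gives 64 per arm for mean pain of 4.0 against 3.0, SD 2.0, significance level 0.05 and 80% power. Sidedness is not stated; two-sided is assumed here. The normal approximation is n = 2 × (1.960 + 0.842)² × 2.0² / 1.0² = 62.8, so 63. The exact two-sample t calculation gives 63.8, so 64. The figure reproduces, as do the other five rows of the table. Planned accrual is 134 to obtain 128 complete data sets, an allowance of 134 − 128 = 6, or 6/134 = 4.5%.

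**2. The rules side by side, for a woman enrolled and later found ineligible.**

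| Source | Her data |
|---|---|
| 9.1 | Destroyed |
| 1, Human Subjects | Retained |
| 4.4.1 with 4.4.2, if she is withdrawn for this reason | Not removed |
| 7.3, if randomised | In the primary and secondary analyses |
| 8.2 | All adverse events recorded |
| 9.4 | Required records kept |

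The first two rows contradict each other directly. The third takes two steps: 4.4.1 makes late-found ineligibility a possible reason for withdrawal, and 4.4.2 then governs the data of anyone withdrawn. Section 9.1 is the only one of these that points to destruction.

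**3. When ineligibility comes to light.** Consent precedes surgery. Randomisation is at surgery, and since the pharmacy prepares the solution according to the allocation, it must precede the injection. Section 5.4 puts the injection after the pocket is made and irrigation is finished. Section 1.5 puts it before the expander goes in. That gives three cases.

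- *Found before randomisation.* She is not in the 7.3 set. The two retention sentences still disagree about her, but no analysis is affected.
- *Found after randomisation, before injection.* She is in the 7.3 set. Her research data would be mainly the preoperative questionnaires.
- *Found after injection.* She is in the 7.3 set and has been exposed if assigned BTX-A. The expander may prove impossible to place, or an exclusion criterion in 4.2 such as recent Botox use may emerge later. Adverse-event data, and perhaps postoperative scores, would exist to be destroyed.

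Section 9.1 exempts none of these women.

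**4. Effect on power.** The documents give no ineligibility rate, so the number of records lost, k, is an assumption. Exact-t power at difference 1.0 and SD 2.0, with the loss split evenly between arms:

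| k | Analysed | Power |
|---|---|---|
| 0 | 134 | 81.9% |
| 6 | 128 | 80.1% |
| 10 | 124 | 78.9% |
| 13 | 121 | 77.9% |

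Assumed rates of 2% and 5% would give 0.02 × 134 = 2.7 and 0.05 × 134 = 6.7 women, about 3 and 7. Even k = 13 costs only 81.9 − 77.9 = 4.0 percentage points.

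**The case against.** Several limits on the point stand.

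- *Frequency.* A reader might infer from 4.4.1 that ineligibility is expected to surface in theatre. The text gives that only as an example. Most exclusion criteria in 4.2 can be checked before surgery, and the pregnancy test precedes enrolment (4.3).
- *Sample size.* It is tempting to set 7 destroyed records against the allowance of 6 and call the study underpowered. The documents do not support this. The allowance protects complete data sets, and a woman whose reconstruction could not proceed has no expansion-phase scores under either rule. Retaining her record does not restore a complete data set.
- *Reconstruction.* A reader might also infer that the randomised population could never be rebuilt. That goes too far. The research pharmacy holds the randomisation (5.3, 5.8), drug use is reconciled (5.9.3, 5.9.4), and hospital charts and dispensing records are source documents (9.2). Unless 9.1 reaches those as well, women could still be counted by arm. What would be lost is the study questionnaire and adverse-event data.
- *Indirect third limb.* Section 4.4.2 reaches these women only through the permissive wording of 4.4.1. The direct conflict is between two sentences.

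None of this removes the contradiction. The objection that 8.2 and 9.4 already pull against destruction is true, but it adds to the list of provisions that 9.1 contradicts; it does not limit what 9.1 says.

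**Conclusion.** The plan is wrong as written. Two near-identical paragraphs give opposite orders for the same women, and the destruction order also conflicts with 7.3, 8.2 and 9.4, and with 4.4.2 for any woman withdrawn as ineligible. The consequence is conditional: it arises for women found ineligible after randomisation, and it reaches safety data on exposure only for those injected. For them, following 9.1 would be an irreversible exclusion after randomisation, with loss of study questionnaire and adverse-event data.

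The number affected is unknown because the documents give no rate. The power effect is small across the range shown, and the case does not rest on it. The conclusion assumes only that 9.1 means what it says and covers women already randomised, from which nothing in the text exempts them.

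**What to change.** Delete the last sentence of the Confidentiality Safeguards paragraph in 9.1 and let the Introduction and 4.4.2 govern. State that coded data on every randomised woman are retained, that she stays in the all-randomised set of 7.3, and that the number found ineligible after randomisation is reported by arm with reasons. Outcome scores she does not have would fall under the missing-data approaches in 7.2. Confine destruction to the pre-enrolment screening information already described in 4.3.

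The cost is one sentence removed and a short clarification added, with no extra patients, visits or procedures.
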